2.0 Background/Scientific Rationale

- *Describe the research problem and provide rationale for the research.*

The goal of the proposed research is to achieve a major advance in promoting effective and efficient delivery of pediatric occupational therapy services for young children with developmental disabilities. To evaluate PEM-Plus usability (Aim 1), ten parents will be recruited to perform tasks related to navigating the PEM-Plus interface. Data on completion rate and time, and user satisfaction, will be analyzed to guide PEM-Plus improvements. Then, in Aim 2, we will examine the feasibility and scientific basis for using the revised PEM-Plus to improve goal setting, care plan development, and parental self-efficacy. Study results will yield a final version of PEM-Plus that is ready for larger-scale testing in a pediatric efficacy trial. This project is aligned with the newly released AOTF research priority of improving care coordination towards improved participation in meaningful activities.

- *Briefly summarize prior experience and/or history relevant to the research.*

Members of our research team pioneered some of the first participation and environment measures that are commonly used in pediatric research and practice (Sections 1.3 and 1.4). The PEM approach represents a significant departure from prior efforts to measure children's participation because we explicitly combined the assessment of children's participation and environment within the same instrument. Development of a web-based application to help parents participate in planning their child's care is a highly innovative and logical next step for our research team. To our knowledge, no other group has developed a web-based application to empower and assist parents in developing their own solutions to promote their child's participation. We expect that PEM+ can advance the quality and efficiency of care planning in pediatric occupational therapy to achieve participation-level outcomes. Our multi-site, transnational research team has established an 8-year track record of continuous extramural funding. We developed and tested the PEM-CY and YC-PEM for research purposes and built a Knowledge Hub to facilitate knowledge uptake and resource exchange about children's participation and environment among key stakeholders (researchers, parents, and providers). We believe that PEM+ will significantly improve the uptake of the PEM approach in practice.

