We will build on Aim 1 recruitment strategies to recruit 24 parents of children with developmental disabilities ages 0-3 years for PEM+ feasibility testing. The sample size estimate is similar to prior studies on participation outcomes (Verhoef, Miedema, Van Meeteren, Stam, and Roebroeck, 2013) and feasibility considerations. We will target recruitment of children in 1 age group (infants and toddlers between 0-3 years) to examine the feasibility of PEM+. Inclusion criteria: Same as Aim 1.

Automated email with study flyer will be sent to families on listserves. Parents who meet eligibility criteria will be directed via web link to create a user account to enter the YC-PEM study platform that is being hosted on REDCap at UIC. Participants will provide online consent and then proceed in completing a demographic questionnaire and YC-PEM online to receive a summary report, followed by phone consultation to interpret their report. Participants will then click a web link on the YC-PEM report to be directed to a revised PEM+ platform hosted via combination of Amazon cloud and REDCap at UIC. Participants will proceed through PEM+ to apply information from the report to generate participation goals for their child and potential intervention strategies. Parents will be given 4 weeks to develop as many goals and intervention strategies as possible, and they may opt for help using one or more of the following options for support: 1) text-based examples of priorities, goals, and strategies that are accessed by the parent in the PEM+ platform, 2) email coaching support (parent clicks on a link in the platform to email trained UIC staff with questions), and/or 3) phone or video conferencing (Skype) consult that participant can request in the platform, to be provided by master coach ([name]). No more than 6 participants will begin PEM+ each week to ensure feasibility, resulting in a total of 8 weeks for data collection (6 participants/week x 4 weeks/participant). Weekly text-message and email reminders will be issued to all participants to promote retention and completion rates. Final phone consultation and CanChild survey completion will take place at 4 weeks. Each participant will be paid \$80.00 at 4 weeks (\$40.00 prorated payment for completion of no more than 2 weeks).

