Participation and Environment Measure-Plus (PEM-Plus) Care Planning Intervention

NCT Number: 03820011

Date: June 17, 2017

Aim 1 Statistical Plan:

Demographic and usability data were exported via REDCap, and an administrative dashboard for analyses. Demographic characteristics and YC-PEM summary scores were reported for each user. To address the main study question, usability estimates were derived for the total study sample, according to technical effectiveness (PEM+ min-max and mean percent completion rate, mean completion time, and mean task difficulty rating), and USE summary scores (mean and range) for ease of use, ease of learning, and user satisfaction.

Aim 2 Statistical Plan:

All analyses were completed on the total sample and age subgroups (0-3 years, 4-5 years) using SPSS 24.0. The primary study aim was to assess for PEM+ feasibility and acceptability. To assess for PEM+ feasibility, retention rate, median completion time of first iteration, median completion time of subsequent interactions, and use of tiered support were reported. To assess for PEM+ acceptability, total scores were reported as means with standard deviations. Additionally, open-ended responses were independently coded by four research team members to sort caregiver feedback regarding the acceptability of PEM+ into categories.

As a secondary aim, preliminary effects mean self-efficacy item scores were calculated and Pearson correlations were used to ascertain associations between proportion of care plans created, relative to areas of desired change, with caregiver self-efficacy scores.

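### Does the correlation of the care-plan proportion with self-efficacy need adjustment for the number of areas of desired change, and a confidence interval?

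*SAP*

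**What the plan says.** The Aim 2 Statistical Plan in the SAP gives the secondary analysis in one sentence. It says that "preliminary effects mean self-efficacy item scores were calculated" and then that "Pearson correlations were used to ascertain associations between proportion of care plans created, relative to areas of desired change, with caregiver self-efficacy scores". It states no covariate, confidence interval, significance level or hypothesis for this analysis. Protocol sections 9.0 and 12.0 contain only template prompts, so they add nothing.

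Protocol section 6.0 supplies the setting. The intention is to "recruit 24 parents of children with developmental disabilities ages 0-3 years for PEM+ feasibility testing", and the justification is that "The sample size estimate is similar to prior studies on participation outcomes". On time: "Parents will be given 4 weeks to develop as many goals and intervention strategies as possible". On sequence: "Participants will provide online consent and then proceed in completing a demographic questionnaire and YC-PEM online to receive a summary report", after which "Participants will then click a web link on the YC-PEM report to be directed to a revised PEM+ platform". The YC-PEM therefore comes before PEM+, but no sentence says that the areas of desired change are counted from it.

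Protocol section 2.0 says Aim 2 will "examine the feasibility and scientific basis for using the revised PEM-Plus to improve goal setting, care plan development, and parental self-efficacy".

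**The concern.** The exposure is a ratio, and dividing by the number of areas does not by itself make it independent of that number. With a fixed four-week window, a parent with many areas may draft about as many plans as a parent with few, and so score a lower proportion. If many areas also go with lower self-efficacy, the number of areas confounds the correlation and pushes it upwards.

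This is the only association analysis in the SAP, and self-efficacy is one of the things the protocol hopes PEM+ will improve. A spurious positive r, reported without an interval, could be taken as early evidence of benefit when a later efficacy trial is planned. The text describes no baseline self-efficacy measure that would help separate the explanations. If areas were counted during PEM+ use and not before it, the ratio would be harder still to interpret.

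**Working it through.** **Inputs.** From the documents: 24 parents, a four-week window, a Pearson correlation, YC-PEM before PEM+. Everything else is assumed: the distribution of areas, about three plans per parent where time limits them, correlations between areas and self-efficacy of -0.3 and -0.5, and a two-sided 5% test as a yardstick, since the SAP sets none.

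**1. The plan's own figure.** The 24 rests on precedent and feasibility. No effect size, power or precision is stated, so there is nothing to reproduce.

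**2. Precision.** The Fisher interval is tanh(atanh r ± 1.96/√(n - 3)), with n - 4 for a partial correlation on one covariate. For r = 0.30 and n = 24, atanh r = 0.310.

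- Pearson: 0.310 ± 1.96/√21 = 0.310 ± 0.428, so r from -0.12 to 0.63.
- Partial: 0.310 ± 1.96/√20 = 0.310 ± 0.438, so r from -0.13 to 0.63.
- Correlation detectable with 80% power: tanh((1.96 + 0.842)/√21) = tanh(0.611) = 0.55.

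On its face this analysis can only be preliminary.

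**3. How the artefact arises.** Write q for the ratio, a for areas, s for self-efficacy. The partial correlation is (r_qs - r_qa·r_as)/√((1 - r_qa²)(1 - r_as²)). If it is zero, r_qs = r_qa·r_as, so both factors must be non-zero for a distortion.

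With areas about Normal(8, SD 3) and plans Poisson(3) capped at areas, simulation (20,000 samples of 24) gives r_qa = -0.54.

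| r_as | Product -0.54 × r_as | Simulated mean r | Rejection, planned r | Rejection, partial |
|---|---|---|---|---|
| 0 | 0 | 0.00 | 5% | 5% |
| -0.3 | 0.16 | 0.16 | 12% | 5% |
| -0.5 | 0.27 | 0.27 | 26% | 5% |

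With plans proportional to areas (binomial, 0.4 per area), r_qa is 0.00, mean r is about 0 and rejection is 5% to 6%.

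**4. Wider range.** Over four distributions of areas at n = 24, for r_as = -0.3 and -0.5:

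- Three time-limited plan models: mean r 0.15 to 0.26 and 0.26 to 0.43; rejection 11% to 24% and 23% to 60%.
- Plans partly rising with areas: rejection 6% to 7% and 8% to 11%.
- Plans proportional to areas: rejection 5% to 6%.

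The largest figures need both unestablished conditions in a strong form.

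**5. Would adjustment repair it?**

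- The 5% rejection for the partial correlation relies on self-efficacy being linear in areas. In the time-limited models, if it is linear in log(areas) the partial rejects in up to about 7% of samples; if in 1/areas, up to about 13%, with mean partial r up to 0.17.
- If areas are set during use (areas = plans + Poisson(4·exp(-b·s)), plans unrelated to s), the planned r rejects in about 49% (b = 0.3) and 86% (b = 0.5). The partial still rejects in about 24% to 25% and 43%.
- If the ratio truly matters (assumed 0.5 SD of self-efficacy per 0.2 in the ratio) and plans are time-limited, power falls from 86% to 70% at n = 24 and from 74% to 55% at an assumed n = 18. With proportional plans at n = 24 it falls only from 54% to 52%.
- Under pure confounding with time-limited plans, the partial r stays at least half the planned r in 29% to 73% (r_as = -0.3) and 14% to 46% (r_as = -0.5) of samples with a significant positive planned r. How far r moves on adjustment is a weak guide at this size.

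**The case for a change.** The strongest case for a change is that the omissions are real and cheap to fill. The fixed window is part of the trial's own design, so a falling ratio is plausible. The partial correlation uses only data already needed to form the ratio, and it would sit beside the planned r without replacing it. An interval would help whether or not there is confounding. The source and timing of the areas are also needed to interpret the ratio at all.

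The omissions stand, as does the mechanism as a possibility. What does not follow is a needed amendment. The partial correlation answers a different question (planning at a fixed number of areas), no decision would hang on it, and whether it is even valid depends on when the areas are counted. The interval can be worked out by any reader from r and the number analysed. The count's source and timing are missing detail. The natural reading is a count from the YC-PEM, whose report parents apply when setting goals, and the protocol lists that questionnaire as an appendix whose content is not in the text available.

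A non-causal description is already what the SAP offers: it speaks of associations and preliminary effects. Section 2.0 of the protocol does speak of improving self-efficacy, but the analysis sentence makes no such claim. The SAP is also written in the past tense, which suggests the analysis is complete; an added correlation would then be post hoc.

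**Conclusion.** The concern identifies a possible confounder but shows no error. Distortion needs the ratio to fall as areas rise and self-efficacy to vary with areas; the documents give neither relation. Where both are assumed, with plans limited by time, the spurious mean r is about 0.15 to 0.43 at n = 24. Where either is absent it is about zero. These sizes rest wholly on assumed inputs.

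The planned Pearson r is a correct description of what the SAP sets out to describe. Adjustment is a fair trade-off that the sponsor may decline: it removes the bias only if self-efficacy is about linear in areas and areas are fixed before PEM+ use, and it can cost up to 16 points of power at n = 24 (86 - 70) in the cases examined. Giving the interval and stating how areas were counted is ordinary good reporting that an analyst would supply when writing up. Neither alters a result, and the primary feasibility and acceptability analyses do not use this correlation. The plan can stand as it is.
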